17. SUBSET OF ANALYSES AT THE INTERIM

The two objectives of the interim analysis are to determine if gantenerumab OLE treatment results in clinical benefit and determine the extent of amyloid removal compared to the double-blind period. The primary analyses for the interim will be the primary analysis of CDR Global

Author: [REDACTED]

Version Number:

7

Version Date:

07Dec2023

Template No.: CS TP BS016 Revision 6

Reference: CS WI BS005

Effective Date: 02Dec2019

(in Section 16.2.3.2) and CDR-SB (in Section 16.2.3.1) applied to subjects who are asymptomatic at baseline for the All Gant Exposure mITT and main set controls.

The following subset of analyses will be conducted separately for baseline asymptomatic and baseline symptomatic subjects, except where noted for select imaging and fluid biomarker analyses, at the interim analysis and additional exploratory analyses will be conducted as needed, noting that focus will be on Year 2 findings in the absence of Year 3 findings, with any imputation for Year 3 excluded. These analyses will be conducted for the each of the three mITT populations and controls as specified for each model, unless the associated section describes the analysis as being conducted on select mITT populations, noting that when multiple models are described within a section, only the first one will be conducted for the interim unless otherwise specified. By-visit descriptive statistics during OLE will be displayed, overall and by OLE baseline symptomatic status, for each associated parameter, including each component of the OLE cognitive composite.

[REDACTED] [REDACTED]

Author: [REDACTED]

Version Number: 7

Version Date: 07Dec2023

Template No.: CS_TP_BS016 Revision 6

Reference: CS_WI_BS005

Effective Date: 02Dec2019

Table B: Interim Analysis Models

Endpoint	Analysis Tier and Statistical Method	Objective
CDR Global	Primary: 16.2.3.2: Cox proportional hazards time to first progression	To evaluate whether the treatment delays the disease progression
	Sensitivity: 16.2.4.2 (third paragraph): post-baseline PiB-PET SUVR normal	To evaluate whether normal / abnormal amyloid levels are associated with lower risk of first progression (delay of disease progression) in CDR Global compared to all controls
	Sensitivity: 16.2.4.1.1 (third paragraph): comparison to concurrent and non-concurrent controls	To evaluate whether the treatment delays the disease progression in CDR Global compared to the concurrent and non-concurrent controls
CDR-SB	Primary: 16.2.3.1: Cox recurrent event proportional hazards model	To evaluate whether the treatment is associated with lower risk of recurrent progression (delay of disease progression) in CDR-SB compared to all controls

Author: [REDACTED]

Version Number:

7

Version Date:

07Dec2023

Template No.: CS_TP_BS016 Revision 6

Reference: CS_WI_BS005

Effective Date: 02Dec2019

Endpoint	Analysis Tier and Statistical Method	Objective
	Secondary: 16.2.3.3: LME model	To evaluate whether the treatment will slow down annual rate of change of CDR-SB compared to all controls
	Sensitivity: 16.2.4.1.1 (both analyses in second paragraph): post-baseline PiB-PET SUVR normal	To evaluate whether normal / abnormal amyloid levels are associated with lower risk of recurrent progression (delay of disease progression) in CDR-SB compared to all controls
	Sensitivity: 16.2.4.1.1 (third paragraph): comparison to concurrent and non-concurrent controls	To evaluate whether the treatment is associated with lower risk of recurrent progression (delay of disease progression) in CDR-SB compared to the concurrent and non-concurrent controls
OLE Cognitive Composite	Secondary: 16.2.3.3: LME model	To evaluate whether the treatment will slow down annual rate of change of OLE Cognitive Composite compared to all controls

Author: [REDACTED]

Version Number:

7

Version Date:

07Dec2023

Template No.: CS_TP_BS016 Revision 6

Reference: CS_WI_BS005

Effective Date: 02Dec2019

Endpoint	Analysis Tier and Statistical Method	Objective
FAS	Secondary: 16.2.3.3: LME model	To evaluate whether the treatment will slow down annual rate of change of FAS compared to all controls
MMSE	Secondary: 16.2.3.3: LME model	To evaluate whether the treatment will slow down annual rate of change of MMSE compared to all controls
Amyloid PET SUVR	Secondary: 16.1.3: MMRM (asymptomatic and symptomatic combined)	To evaluate whether gantenerumab can stop or reverse amyloid plaque growth during the OLE period for all participants
	Secondary: 16.1.4.1: MMRM (asymptomatic and symptomatic combined)	To compare the gantenerumab treatment effect during OLE period by the double-blind treatment (gantenerumab, combination of solanezumab and placebo)
	Secondary: 16.1.4.2: MMRM	To evaluate whether gantenerumab can stop or reverse amyloid plaque growth during the OLE period for asymptomatic and symptomatic separately

Author: [REDACTED]

Version Number:

7

Version Date:

07Dec2023

Template No.: CS_TP_BS016 Revision 6

Reference: CS_WI_BS005

Effective Date: 02Dec2019

Endpoint	Analysis Tier and Statistical Method	Objective
	Secondary: 16.1.4.3: MMRM	To evaluate the treatment effect of gantenerumab in reducing or reversing amyloid plaque growth during the whole study duration for all participants treated with gantenerumab in double-blind, overall and for asymptomatic and symptomatic separately
	Secondary: 16.1.4.4: Fisher's exact test	To evaluate whether treatment with gantenerumab is associated with a shift from baseline abnormal to post-baseline normal
MAC-Q	Secondary: 16.2.3.3: LME model	To evaluate whether the treatment will slow down annual rate of change of MAC-Q compared to internal controls
Tau PET SUVR	Secondary: 16.2.3.3: LME	To evaluate whether gantenerumab can reverse the annual rate of amyloid plaque growth compared to internal controls

Author: [REDACTED]

Version Number:

7

Version Date:

07Dec2023

Template No.: CS_TP_BS016 Revision 6

Reference: CS_WI_BS005

Effective Date: 02Dec2019

Endpoint	Analysis Tier and Statistical Method	Objective
FDG-PET SUVR	Secondary: 16.2.3.3: LME	To evaluate whether gantenerumab can reverse the annual rate of amyloid plaque growth compared to all controls
CSF Amyloid Beta1-42/40	Secondary: 16.2.3.5: MMRM (asymptomatic and symptomatic combined)	To evaluate whether the treatment will show an increase from baseline in CSF Amyloid Beta 42/40
CSF Total Tau	Secondary: 16.2.3.5: MMRM (asymptomatic and symptomatic combined)	To evaluate whether the treatment will show a decrease from baseline in CSF Total Tau
CSF pTau217	Secondary: 16.2.3.5: MMRM (asymptomatic and symptomatic combined)	To evaluate whether the treatment will show a decrease from baseline in CSF ptau217
CSF MTBR243	Secondary: 16.2.3.3: LME model	To evaluate whether the treatment will slow down annual rate of change of MTBR243 compared to all controls

Author: [REDACTED]

Version Number:

7

Version Date:

07Dec2023

Template No.: CS_TP_BS016 Revision 6

Reference: CS_WI_BS005

Effective Date: 02Dec2019

Kaplan-Meier figures will be created for asymptomatic subjects for each of the three mITT populations and associated controls for both the CDR Global time to first progression and CDR-SB time to recurrent progression. Figures of model estimated mean over time by treatment arms with spaghetti plots of individual data over time of CDR-SB will be provided for asymptomatic subjects for each of the three mITT populations.

The following biomarkers are considered the most relevant to the mechanism of action of gantenerumab: Tau PET SUVR, CSF pTau217 and CSF MTBR243. Analyses using LME and MMRM of additional CSF biomarkers, additional clinical/cognitive parameters, and select plasma biomarkers which are not listed in [Table B](#) will be assessed as exploratory analyses by Washington University, with planned analyses to be described in the Addendum of the Statistical Analysis Plan written and signed prior to the availability of data to Washington University, and associated items will not be run by [REDACTED] for the interim analysis. Analyses of CDR-SB described in [Sections 16.2.4.1.4](#) (exponential disease progression model), [16.2.4.1.5](#) (logistic disease progression model), and [16.2.4.1.6](#) (longitudinal logistic regression model) may also be assessed as exploratory analyses by Washington University and will not be run by [REDACTED] for the interim analysis. Any exploratory analyses, including those planned as noted above, will be included in any reports written to summarize the interim analysis only when considered relevant and will be identified as exploratory analyses.

[REDACTED] [REDACTED]

Author: [REDACTED]

Version Number: 7

Version Date: 07Dec2023

Template No.: CS_TP_BS016 Revision 6

Reference: CS_WI_BS005

Effective Date: 02Dec2019

18. SAFETY OUTCOMES

All outputs for safety outcomes will be based on the SAF.

There will be no statistical comparisons between the treatment groups for safety data, unless otherwise specified with the relevant section.

18.1. ADVERSE EVENTS

Adverse Events (AEs) will be coded using MedDRA SOC and PT. The version will be established and documented prior to lock of the data and will be identified within footnotes.

An AE is defined as any untoward medical occurrence in a clinical trial subject, regardless of whether it is considered to be drug related. AEs will be recorded and assessed as to whether they are TEAEs. TEAEs are defined as events that first occur or worsen (increase in severity) after the first dose of the OLE study drug. The onset date/time of an AE will be compared to the date/time of first dose of the OLE study drug to determine if the AE is treatment emergent or not. If the AE onset date is missing or partial, the date will be compared as far as possible with the date of first dose of the OLE study drug. AEs will be assumed to be treatment-emergent unless there is clear evidence (through comparison of partial dates and/or collected assessment of whether the AE started prior to the first dose of the study drug) suggesting the AE started prior to the first dose of OLE study medication.

An overall summary of TEAEs will be presented with the number and percentage of subjects having a TEAE, number of TEAEs by severity, number of subjects with a TEAE by highest severity, a TEAE related to study treatment, an injection site reaction TEAE, a serious TEAE, a

Author: [REDACTED]

Version Number:

7

Version Date:

07Dec2023

Template No.: CS_TP_BS016 Revision 6

Reference: CS_WI_BS005

Effective Date: 02Dec2019

TEAE leading to treatment discontinuation, a TEAE leading to study discontinuation, and an AE with an outcome of death. An overall summary of TEAEs will also be presented by dose level.

Subjects experiencing more than one TEAE by SOC and PT will only be counted once at the preferred terminology level in AE frequency tables, but each unique TEAE will be included in the total number of TEAEs (where provided) for each SOC and PT. The overall summary for SOC and PT will be presented overall. A separate table summary will also be reported by dose level.

In summaries presented by SOC and PT, SOC will be sorted by alphabetical order within SOC, then PT.

A listing will include TEAEs and Non-TEAEs. Events ongoing from the double-blind period and events reported in the open label period will be listed separately

18.1.1. ALL TEAEs

18.1.1.1. Severity

Severity is classed as mild/ moderate/ severe (increasing severity). TEAEs starting after the first dose of OLE study medication with a missing severity will be classified as severe.

18.1.1.2. Relationship to Study Medication

Relationship, as indicated by the Investigator, is classed as “Definite”, “Probable/Likely”, “Possible”, “Unlikely”, “Definitely Not” (decreasing severity of relationship). A “related” TEAE is defined as a TEAE with a relationship to study medication as “Definite”, “Probable/Likely” or

Author: [REDACTED]	Version Number:	7
	Version Date:	07Dec2023
Template No.: CS_TP_BS016 Revision 6	Reference:	CS_WI_BS005
Effective Date: 02Dec2019		

Copyright © 2009, 2010, 2012, 2016, 2018, 2019 [REDACTED] All rights reserved. The contents of this document are confidential and proprietary to [REDACTED] Holdings Inc. and its subsidiaries. Unauthorized use, disclosure or reproduction is strictly prohibited.

“Possible” to study medication. TEAEs with a missing relationship to study medication will be regarded as related to study medication. If a subject reports the same AE more than once within that SOC/ PT, the AE with the worst case relationship to study medication will be used in the corresponding relationship summaries.

18.1.2. TEAES LEADING TO TREATMENT TERMINATION

TEAEs that lead to treatment termination will be presented by a listing. TEAEs leading to treatment termination are those which are recorded as “Drug Withdrawal” for action taken with study treatment on the OLE AE page of the eCRF. The subject’s ID number, the TEAE that caused treatment termination, and date of withdrawal will be included in the listing.

18.1.3. TEAES LEADING TO STUDY DISCONTINUATION

TEAEs that lead to study discontinuation will be presented by a listing and are determined using the question “Did the AE cause the subject to discontinue from the study?” on the OLE AE page of the eCRF. The subject’s ID number, the TEAE that caused the study discontinuation, and date of discontinuation will be included in the listing.

18.1.4. SERIOUS ADVERSE EVENTS

An SAE is any AE which meets any of the following criteria:

- Death of subject
- Life-threatening
- Inpatient hospitalization or prolongation of existing hospitalization
- Persistent or significant disability/incapacity
- Important medical event requiring medical or surgical intervention to prevent

Author: [REDACTED]

Version Number:

7

Version Date:

07Dec2023

Template No.: CS_TP_BS016 Revision 6

Reference: CS_WI_BS005

Effective Date: 02Dec2019

serious outcome

- Congenital anomaly/birth defect
- Suspected Hy's Law Case
- Other (otherwise medically significant)

The SAE will be presented by a listing. The subject's ID number, SOC, PT and verbatim term and SAE onset/stop date will be included in the listing. Treatment Emergent SAEs will be summarized by SOC and PT.

18.1.5. INJECTION SITE REACTIONS (ISRs)

Injection site reactions related to study treatment will be recorded as injection site reactions on the AE CRF page, with signs and symptoms (e.g., swelling, redness) collected separately. The signs and symptoms associated with ISRs will be coded in the same manner as other AEs and will be summarized separately from other events, with summaries by SOC and PT consistent with the overall summary of AEs.

18.1.6. OTHER CAUSES OF ADVERSE EVENTS

The other causes of AEs include:

- AE involving the injection/infusion site
- AE occurring due to administration of PIB
- AE occurring due to administration of FDG
- AE occurring due to administration of [¹⁸F] AV-1451 Tau PET

The relationship of an AE to these causal factors will be presented in the same manner as described for relationship to study drug. The other causes of AEs will be summarized by cause and by relationship.

Author: [REDACTED]

Version Number:

7

Version Date:

07Dec2023

Template No.: CS_TP_BS016 Revision 6

Reference: CS_WI_BS005

Effective Date: 02Dec2019

18.2. DEATHS

A listing of all deaths will be provided.

18.3. SAFETY MRI EVALUATIONS

The number and percentage of subjects with MRI scan (including annual, safety, and dose titration MRIs) conducted will be summarized by visit for each type of MRI finding during the OLE. Summaries will also display the number of subjects with a new finding and those with any post-baseline finding for each type of MRI finding.

ARIA can occur as either cerebral edema (ARIA-E) or as hemorrhages (ARIA-H), typically microhemorrhages, but larger hemorrhages and frank infarction have also been reported. MRI scans will be analyzed for ARIA changes at the Mayo Clinic Aging and Dementia Imaging Laboratory. The number of microhemorrhages (ARIA-H, including both hemorrhages and hemosiderin deposits) and size of areas of edema (ARIA-E) will be monitored at entry and throughout the trial.

Frequencies and percentages of ARIA-E will be summarized by dose (all doses), by visit, and for the highest post-baseline value. Frequency and percentage of ARIA-H will be summarized by dose separately for ARIA-H Microhemorrhages and ARIA-H Superficial Siderosis, with summarizes separated for those associated with ARIA-E and those which are not. The number of ARIA-H and ARIA-E will be categorized (1, 2 to 4, 5+, or no presence). The size of ARIA-E, where present, will be summarized using mean (SD) by visit. A summary of time to ARIA-E resolution will be presented. ARIA-E resolution corresponds to the first MRI following a new post-baseline ARIA-E finding where no definite findings are observed and is calculated as the date of the MRI with no findings – the date of the MRI with AREA-E +1 day. If a subject has

Author: [REDACTED]

Version Number:

7

Version Date:

07Dec2023

Template No.: CS_TP_BS016 Revision 6

Reference: CS_WI_BS005

Effective Date: 02Dec2019

more than one ARIA-E that resolves, the largest duration per subject will be used for the summary of time to ARIA-E resolution. A listing of all ARIA-E findings will be produced for all subjects who have an incidence of ARIA-E at any assessment. The listing will include the number of definite findings for ARIA-E, the size of ARIA-E, the number of days since treatment start, the current active drug dose, and the number of days since start of the current active drug dose. In addition, the frequencies and percentages of the following findings will be summarized in separate tables by visit and for the highest post-baseline value:

- Large cortical infarctions
- Small cortical infarctions
- Subcortical infarctions
- Acute ischemia infarctions
- Other findings (frequencies and percentages only, including for individual sub-categories)

MRI findings will be listed. Details for other findings will be listed separately for all subject with other MRI findings at any assessment. The listing will include number of definite other findings, a description of the other findings, number of days since treatment start, current active dose and the number of days since start of the current active dose.

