1.5.2 Open-Label Extension (1500 mg Q2W, G4 Formulation)

1.5.2.1 Dose Regimen

The initial target dose in the OLE period was CCI

Unless otherwise stated,

gantenerumab product used within the OLE study period refers to the G4 formulation.

The dose will be slowly increased via multiple titration steps similar to that used in the double-blind period of the trial. Participants will follow the previously established OLE titration schedule to reach CCI by receiving CCI doses at each titration step; CCI CCI CCI and then CCI. After C doses at CCI, the dosing frequency will increase to CCI and participants will receive CCI for 12 weeks, and then the final, target dose of CCI thereafter (Figure 1). The entire dose titration period will take 15 months. At some sites, participants may have received 3 or more doses at CCI before regulatory approval and consenting to Amendment 11 is completed. Those participants will proceed to initiate titration beyond CCI as soon as approvals are in place.

For the study drug administration visits following the occurrence of a safety MRI, the site principal investigator or designated sub-investigator must review the MRI central read prior to proceeding with the subsequent dose administration.

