2.2 Open-Label Extension: Drug Treatment Regimen

All participants participating in the OLE will receive gantenerumab produced with the G4 process. The pharmacokinetic behavior of the old (G3) and the new (G4) process were compared in a relative bioavailability study. The plasma exposure in terms of AUC_{inf} was approximately 1.18-fold higher after SC administration of 600 mg gantenerumab G4 compared to 600 mg gantenerumab G3, whereas C_{max} were similar. Based on these results, the dosing regimen of the Phase III program in sporadic AD (WN29922 and WN39658) has been adjusted by a factor of 1.18.

In DIAN-TU-001, all OLE participants will restart titration, starting at a dose of [REDACTED] of drug product administered SC approximately every [REDACTED]

Participants will initiate up-titration following 3 doses at the [REDACTED] level and a safety MRI approximately 1 week after the [REDACTED] dose of [REDACTED]. Participants will receive at least 3 doses at each titration step, [REDACTED] (+9 days) apart, before proceeding to the next titration step. Advancement to the next titration step is guided by the ARIA-related intervention algorithm for dose titration (see tables in Section 1.14). The dose titration and safety MRI schedule is provided in Table 5. The target maximum dose for all participants is [REDACTED] [REDACTED]. Participants will dose escalate/titrate up to [REDACTED] receiving at least 3 doses at each titration step. After three (3) doses at [REDACTED] apart, participants will continue to escalate to [REDACTED] [REDACTED] for 6 doses and then to the maximum target dose of [REDACTED]

Participants will continue dosing for up to 156 weeks. The total number of doses may vary by participant based on dosing compliance and/or ARIA intervention.

Table 5 DIAN-TU-001 Gantenerumab OLE Titration Safety MRI Schedule

- ^a OLE safety MRI schedule. A safety MRI will be scheduled 1 week (\pm 4 days) after the third dose of each CCI titration step CCI unless otherwise indicated by the ARIA-E and ARIA-H management algorithms (Section 1.14). If an annual visit follows the third dose of a titration step, the annual MRI assessment can fulfill this requirement as long as the MRI reading is reviewed prior to dosing at that visit.

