- Lumbar Puncture (LP) should be conducted as close to the participant's double-blind CCI [REDACTED]
- Annual MRI (including structural and functional MRI) uploaded immediately to ensure reading obtained prior to dosing. This MRI includes safety MRI sequences. MRI should be performed before lumbar puncture, if on the same date.
- Drug product dosing and post-dose monitoring/evaluation as specified in Section 2.5 for OLE V13 and OLE V27; no drug administration should occur at OLE V40 or an early termination visit.
- Follow-up phone call or brief visit within 24 hours after LP, and no longer than 48 hours later, to review any adverse events.

3.2.6 OLE Visits 20 and 33

Location: DIAN-TU site or participant's home or other trial-identified location with the trial-designated home health nurse.

Timing: 76 and 128 weeks \pm 3 days from day of first dose at OLE Visit 1. The second dose administration for Q2W dosing associated with each visit should be completed at weeks 78 and

130 ± 3 days, respectively, and will include vitals, concomitant medications, and AEs as outlined in the Schedule of Visits.

Procedures:

- Cognitive Battery Subset (Section 3.2)
- Mini-Mental State Examination (MMSE)
- Concomitant medication review
- Adverse event assessment
- Vital signs (blood pressure, heart rate, respiratory rate, and body temperature; weight may be obtained approximately every 3 months per Section 6.1.6 of the main protocol)
- C-SSRS administration
- Blood collection for the following:
 - Clinical laboratory tests (hematology, chemistry)
 - Stored Plasma
- Urine pregnancy testing for POCBP
- Drug product dosing and post-dose monitoring/evaluation as specified in Section 2.5
- Phone call (not required at all home/off-site visits but direct site-participant contact should occur at least once every 3 months throughout the study): the DIAN-TU site coordinator calls participant and addresses any concerns, discusses scheduling of safety MRI and next visits, and encourages compliance

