9. Serum pregnancy testing will be performed at OLE V1 and the safety follow-up visit. Urine pregnancy testing will be performed at all other monthly visits, i.e. every 4 weeks. Pregnancy tests will be confirmed as negative prior to Q4W dosing with study drug, or prior to every other dose when dosing Q2W. Women who have undergone tubal ligation are also required to have pregnancy tests performed. Alternate tests may be used if urine collection is not feasible but must be approved by the sponsor in advance.
10. Blood pressure, heart rate, respiratory rate, and body temperature will be collected at all visits. Height will be measured at OLE baseline (OLE V1) and annual visits only; weight will be measured approximately every 3 months.
11. Clinical assessments: DIAN-TU clinical assessment battery includes: study partner interview and administration of CDR and supplemental CSR-SB; clinician assessment of **CCI** [REDACTED]
[REDACTED]
[REDACTED].
12. Electrocardiogram (ECG) assessment should be performed locally.
13. See Section 3.2 in this appendix and the arm-specific *DIAN Trials Unit Cognition Core Procedures Manual* for additional details, including visit specific battery information. Cognitive testing should be completed as early in the day as possible, and before study drug infusion or injection.
14. A safety MRI will be scheduled 1 week (\pm 4 days) after the third dose of each **CCI** titration steps **CCI** [REDACTED], and after the sixth dose of the each **CCI** titration step **CCI** [REDACTED] unless otherwise indicated by the ARIA-E and ARIA-H management algorithms (Section 1.14). Once at stable dose (after the annual safety MRI at week 104 (OLE V27) following approximately 22 doses of **CCI** [REDACTED] administered **CCI** [REDACTED]), safety MRIs will be scheduled 1 week (\pm 4 days) after every 12th dose **CCI** [REDACTED] unless otherwise indicated by the ARIA-E and ARIA-H management algorithms). Additional safety MRIs may be scheduled to monitor ARIA-E events (Section 1.13.1).
15. **CCI** [REDACTED]
[REDACTED]
[REDACTED].

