16. All participants enrolled in OLE for gantenerumab will start at the **CCI** [REDACTED] dose **CCI** [REDACTED] and will up-titrate to **CCI** [REDACTED]; then at increased dosing frequency of **CCI** [REDACTED] to a target dose of **CCI** [REDACTED]. Participants should receive at least three doses at each Q4W titration step up to **CCI** [REDACTED] 4 weeks (\pm 4 days) apart, before proceeding to the next titration step. Participants should receive six doses of **CCI** [REDACTED] 2 weeks (\pm 3 days) apart before proceeding to the final titration step of

CCI 2 weeks (\pm 3 days) apart. The titration schema was designed to reach the target dose of **CCI** administered every 2 weeks; however, the target dose may not be achieved as otherwise dictated ARIA-E and ARIA-H management algorithms (Section 1.14) or more conservative action by the site principal investigator/DIAN-TU Medical Monitors. If needed, the schedule of assessments will be adjusted. Dosing visits occurring every 2 weeks will be identified/labeled as one visit. The first portion of the visit will include completion of any required visit procedures and dosing; two weeks \pm 3 days after, the second dose will be administered.

- 17. Site study coordinators should call participants either during or within two weeks after OLE V2 and OLE V3. For OLE V4 and subsequent home visits, coordinator calls can be made with less frequency at the discretion of the PI or designee, and/or coordinator, and participant, but should occur at least every 3 months.
- 18. For OLE V20 and OLE V33, chemistry and hematology are required; no urinalysis is needed.
- 19. A sentinel cohort of the first 20 participants to titrate beyond **CCI** every **C** weeks will have an additional safety MRI performed after the first two doses of **CCI** administered two weeks apart (Week 51, SC1-MRI) prior to up-titrating to **CCI**; and after the first **CC** doses of **CCI** administered two weeks apart (Week 63, SC2-MRI). The DIAN-TU Medical Monitors will review the individual and aggregate data to ensure there are no safety findings warranting more frequent MRI for all participants.
- 20. Any participant not having initiated up-titration at any point should use the MRI label of OSM4 for this safety MRI.
- 21. For plasma collection only at this visit.
- 22. Clinical laboratory tests (hematology, chemistry, urinalysis) at the discretion of the investigator.

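### The by-dose TEAE and ARIA tables report crude percentages although planned time and scans at the target dose far exceed those at a titration step, so the top dose can look riskier with no dose effect

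*SAP*

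**What the plan says.** SAP 18.3 (Safety MRI Evaluations) states: "Frequencies and percentages of ARIA-E will be summarized by dose (all doses), by visit, and for the highest post-baseline value". It plans ARIA-H by dose as well, split into microhemorrhages and superficial siderosis. SAP 18.1 (Adverse Events) adds: "An overall summary of TEAEs will also be presented by dose level". Neither section gives an exposure-adjusted rate, a rate per scan, the denominator for a dose level, or a rule for assigning an event to a dose.

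The dosing schedule is in Protocol Appendix 3. The schedule footnote on dosing reads "Participants should receive at least three doses at each Q4W titration step up to" a redacted level. Section 1.5.2.1 then gives a Q2W step "for 12 weeks, and then the final, target dose of" a redacted amount, and adds "The entire dose titration period will take 15 months". Section 2.2 sets the limit: "Participants will continue dosing for up to 156 weeks".

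SAP 15 reports some exposure: the number of administered doses by dose level, and the duration at each participant's highest dose. The ARIA-E listing in SAP 18.3 shows the current dose and the days since it started.

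**The concern.** A crude percentage rises with the time participants are watched and, for a finding seen on MRI, with the number of scans. If one dose level is observed for much longer than the others, its percentage can be higher when the risk is the same.

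Safety and tolerability at higher doses is a primary endpoint of the extension (Appendix 3, Section 1.9.2), and two titration steps go above doses previously tested (Section 1.6). The protocol already argues from counts by dose: Section 1.5.2.3 says that most double-blind ARIA-E occurred above 900 mg Q4W. A new by-dose table invites the same reading. Scan opportunity matters because most double-blind ARIA-E cases were asymptomatic (7 of 10 in Section 1.5.2.3, 8 of 10 in Section 1.4), so detection depends largely on scanning.

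**Working it through.** **Start of target dosing.** Safety MRIs at weeks 9, 21 and 33 and the annual visit at week 48 (Appendix 3, Sections 3.2.5 and 3.2.9.1) mark the ends of four Q4W steps, each 3 doses × 4 weeks = 12 weeks. One 12-week Q2W step follows. Total: 5 × 12 = 60 weeks, or 60/4 = 15 four-week months, which matches the stated 15 months. The doses are redacted, so this layout is inferred from the schedule.

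**Check against the plan's own figure.** The safety MRI footnote to the schedule places the week 104 scan "following approximately 22 doses of" the target. Q2W doses at weeks 60, 62, …, 102 number (102 − 60)/2 + 1 = 22, which agrees.

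**Time at target against a 12-week step.**
- Full plan: 156 − 60 = 96 weeks, and 96/12 = 8.0.
- To the last dose: Section 3.2.5 says "no drug administration should occur at OLE V40 or an early termination visit". The last planned dose is therefore at week 154, giving 94/12 = 7.8.
- Participant at week 104: 104 − 60 = 44 weeks, and 44/12 = 3.7.
- The formulation table (Table 6) has five dose rows for six schedule steps, so one mg dose may be used at both Q4W and Q2W. That level would then span 24 weeks, and the ratios against it would be 96/24 = 4.0 and 44/24 = 1.8.

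**Regular scans.** Each titration step has one. The target dose has six: weeks 71, 83, 95 and 127, plus the annual scans at 104 and 156. The first 20 participants at each of the last two steps have one extra scan there.

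**Expected percentage with no dose effect.** Assume the same constant hazard of 10% per year at every level. This figure is an assumption and is not in the documents. P(t) = 1 − exp(−0.10 × t/52).

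| Time at level | Expected percentage | Ratio to a 12-week step |
|---|---|---|
| 12 weeks | 2.3% | 1.0 |
| 44 weeks | 8.1% | 3.6 |
| 96 weeks | 16.9% | 7.4 |

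For assumed constant hazards of 2% to 10% per 12 weeks, the ratio runs from 3.6 down to 3.2 at 44 weeks and from 7.5 down to 5.7 at 96 weeks.

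**If risk is front-loaded.** Assume 5% in the first 12 weeks at a level, then a hazard g times as large: P(t) = 1 − exp(−0.0513 × [1 + g(t − 12)/12]), where 0.0513 = −ln 0.95.
- g = 0.25: 8.2% at 44 weeks (ratio 1.6) and 13.2% at 96 weeks (ratio 2.6).
- g = 0: 5.0% at any time (ratio 1.0).

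**With the fix.** Under the equal 10% per year hazard, every level shows 10 first events per 100 person-years at risk, and 2.3% with a first event in the first 12 weeks.

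**The case against.** **The by-visit table already gives an equal-time view of ARIA.** SAP 6.4 summarizes safety and titration MRIs by nominal visit, SAP Appendix 1 labels at least the first of them by dose, and SAP 18.3 counts participants with a new finding. With one regular scan near the end of each step and the next at week 71, about 11 weeks into the target dose, this approximates the wanted comparison. That stands for participants on schedule. It fails for those held at a step by the ARIA rules, and for those whose late consent to Amendment 11 shifts their weeks (Appendix 3, Section 2.2). There is no by-visit counterpart for TEAEs.

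**The SAP does not ignore exposure.** That is correct, and a reader might wrongly infer otherwise. However, the duration summary covers each participant's own highest dose, which need not be the target. The dose counts by level are not linked to events. The ARIA-E listing includes only participants with ARIA-E, so it supplies no denominator.

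**The top dose need not look worse.** A reader might infer that it will, and by seven- or eightfold. The documents do not support this. Eight is the on-schedule, full-plan maximum, and the SAP change log says the extension was terminated early after an interim that SAP 4.3 timed to Year 2 data. Appendix 3, Section 1.4 says that double-blind ARIA-E came generally after two doses of a titration dose, which points towards front-loading. Holding participants with ARIA-E at lower doses may leave lower-risk people at the top. Early stoppers lower the top-dose percentage if the denominator is the whole safety set.

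**The denominator may be in the table templates**, which SAP 8 says define content and which are not in the documents. If so, that part is already met. Safety outputs are also descriptive (SAP 18) and the study report is to be abbreviated, which limits the consequences.

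**Conclusion.** The by-dose percentages mix dose with time observed and, for ARIA, with the number of scans. The plan provides no table that separates them across dose levels. The planned imbalance is up to 8-fold in time, about 3.7-fold for a participant at week 104, and six regular scans against one. These figures assume on-schedule titration in 12-week steps; delays reduce them, as does a mg dose that spans two steps. Actual person-time after early termination is not in the documents.

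The top dose can look riskier with no dose effect: 8.1% or 16.9% against 2.3% under the assumed equal constant hazard of 10% per year. The size depends on that assumption, and the effect disappears if all risk falls in the first 12 weeks at a level. The planned table cannot show which case applies. This is a worthwhile improvement to reporting, not a serious defect, and it implies nothing about which dose or dosing rule is right.

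**What to change.** For each dose level, add to the TEAE, ARIA-E and ARIA-H summaries:
- the number exposed, the person-years and the number of MRI scans at that level;
- first events per person-year with a 95% CI;
- the percentage of those exposed with a first event in the first 12 weeks at that level.

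Assign each event to the dose in use at onset, or at detection for MRI findings. State the denominator, and say whether one mg dose given Q4W and Q2W counts as one level or two.

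The cost is a little more programming, since dosing and MRI dates are already collected. Person-time rates can dilute events that cluster just after a dose step, and the 12-week percentage covers that case.
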